23. History of or currently experiencing a medical condition or any other finding (including laboratory test results) that, in the opinion of the Investigator, might confound the results of the study; pose an additional risk in administering study drug to the subject; could prevent, limit, or confound the protocol-specified assessments; or deems the subject unsuitable for the study.

Additional Exclusion Criteria for Subjects With Asthma

24. Subjects must not have experienced a severe asthma exacerbation (defined as worsening asthma that requires treatment with oral corticosteroids for 3 or more days, or emergency room attendance) or deterioration in asthma requiring an increase in asthma treatment for at least 6 weeks prior to Screening.
25. Subject is receiving more than two maintenance asthma therapies or theophylline preparations for asthma treatment.
26. Pulse oximetry reading of <90% oxygen saturation measured at rest at Screening.

Additional Exclusion Criteria for Subjects With COPD

27. Receipt of theophylline, roflumilast, maintenance oral corticosteroids, or long-term oxygen therapy (defined as prescribed for 12 or more hours per day).
28. Exacerbation of COPD requiring treatment with systemic corticosteroids and/or antibiotics, or emergency room attendance or hospitalization within 6 weeks prior to Screening.
29. More than three COPD exacerbations with the past 12 months.
30. Pulse oximetry reading of <90% oxygen saturation measured at rest at Screening.

Subject Withdrawal: Subjects may be discontinued from the study at any time if the subject, Investigator, or Sponsor determines that it is not in the best interest of the subject to continue participation. Reasons for discontinuation include the following:

- AE
- Lack of efficacy
- Lost to follow-up
- Withdrawal by subject
- Protocol deviation (including noncompliance with study drug or study procedures)
- Pregnancy
- Study terminated by the Sponsor
- Other

Statistical Methods: Detailed statistical analysis will be outlined in the statistical analysis plan, which will be developed and finalized prior to database lock.

Sample Size Considerations: Using a ratio of 1:1, a sample size of 27 subjects per treatment group (54 subjects total) provides 80% power to detect a treatment reduction in TSS AUC of at least 55% from placebo (assuming TSS AUC from the previous Phase 2a clinical challenge study to: mean [standard deviation] of placebo: 500 [450] and EDP-938: 225 [200]) using a t-test with

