5.7.2 Treatment Compliance

The subject will be instructed to bring all study drug (including empty bottles) to the site on Day 3, Day 5, and EOS Visit (for subjects who discontinue study drug or the study early). Both accountability and study drug compliance, including tablet counts and the electronic dosing record (or back-up paper diary as applicable) completed by the subjects, will be reviewed at each study site visit as indicated in the SoA (Appendix 1). The number of tablets will be counted, and

the site staff will ask the subjects why any doses were missed, if applicable. Any potential reasons for lack of compliance with dosing will be monitored and followed up by the site staff. Compliance assessment may be completed at the study site or by a study nurse via a home visit, if feasible; refer to the SPM for details.

The time and date of doses of study drug taken at the study site should be recorded by site staff. From Day 1, subjects will electronically record the time and date that each dose is taken. In case the subject is unable to complete any assessments or recordings into the device for technical reasons, the subject will also be provided with a paper diary(ies) as a back-up.

For any subject considered to demonstrate continued noncompliance of study drug dosing despite continued educational efforts, the Investigator should contact the [REDACTED] or the Sponsor's Medical Monitor to discuss possible discontinuation of the subject from the study.

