7.2 Subject Withdrawal/Early Termination

Subjects may withdraw from the study at any time at their own request, or subjects may be withdrawn at any time at the discretion of the Investigator or Enanta Pharmaceuticals, Inc. for safety, behavioral, or administrative reasons. However, the Investigator should consult with the [REDACTED] Medical Monitor where possible before prematurely removing a subject. For any subject who decides to withdraw from the study, the Investigator should inquire about the reason for withdrawal, request that the subject returns all unused investigational product(s), request that the subject returns for a final study site visit, if applicable, and follow up with the subject regarding any unresolved AEs. Although a subject may discontinue the study drug or the study early, every effort must be made for the subject to return to the site within 24 hours and no more than 48 hours later to complete the EOS procedures.

If a subject withdraws from the study and also withdraws consent for disclosure of future information, no further evaluations should be performed, and no additional data should be collected. Enanta Pharmaceuticals, Inc. may retain and continue to use any data collected before such withdrawal of consent.

Any randomized subjects who withdraw or are withdrawn from the study will not be replaced.

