7.2.1 Withdrawal Criteria

Subjects may be discontinued from the study at any time if the subject, Investigator, or Sponsor determines that it is not in the best interest of the subject to continue participation. Reasons for discontinuation include the following:

- AE
- Lack of efficacy
- Lost to follow-up
- Withdrawal by subject
- Protocol deviation (including noncompliance with study drug or study procedures)
- Pregnancy
- Study terminated by the Sponsor
- Other

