The TSS AUC from Day 1 through Day 14 will be calculated using the trapezoid rule (*Matthews et al., 1990*). The AUC will require at least 2 non-missing calculated total symptom scores. Missing total symptom score data will be reviewed for potential impact, and any decisions to include subjects that fail these criteria above will be documented. The AUC will be calculated based on available individual assessments of TSS collected twice per day from Day 1 through Day 14, and the actual date/time of each assessment will be used for the calculation. For the baseline TSS, the actual time is set as 0. For each assessment post first dose, the actual time in days is computed as difference between the date/time of the assessment and the date/time of the first dose. The AUC is also standardized for 14 days by multiplying  $14/t_{last}$  where  $t_{last}$  is the actual time in days of the last available assessment. Additionally, the AUC from Day 1 through Day 3, the AUC from Day 1 through Day 5, and the AUC from Day 1 through Day 9 will be also derived and standardized similarly as for AUC from Day 1 through Day 14.

The AUC TSS from Day 1 through Day 14 will be compared between EDP-938 and placebo using an analysis of covariance (ANCOVA) model with treatment group, asthma/COPD status (present or absent) as factors and the baseline TSS as a covariate. The analysis will be performed using SAS procedure MIXED. Treatment groups will be compared using a type III sum-of-squares. The least-squares means, standard errors and two-sided 95% confidence intervals (CI) will be presented for individual groups and the difference between groups. The same ANCOVA analysis will be performed for the TSS AUC from Day 1 through Day 3, from Day 1 through Day 5 and from Day 1 through Day 9.

Descriptive statistics will be displayed for TSS and change from baseline by day and timepoint and also for average daily TSS by day and will include at a minimum the number of non-missing measurements, mean, standard deviation, median, minimum, maximum, and 95% CI for the mean.

Multiple line graphs of TSS will be produced:

- (1) Observed mean TSS  $\pm$  95% confidence interval by days 1-14 and timepoint for each treatment group
- (2) Observed mean TSS (average per day)  $\pm$  95% confidence interval by days 1-14 for each treatment group

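### Exit from the study for lack of efficacy or noncompliance is permitted and no diary to Day 14 is provided for afterwards, so the primary symptom score can be cut short for reasons linked to symptoms or behaviour

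*Protocol*

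**What the plan says.** **Who may end participation, and why.** The Protocol Summary and Section 7.2.1 use the same sentence: "Subjects may be discontinued from the study at any time if the subject, Investigator, or Sponsor determines", the required finding being that carrying on would not serve the subject's best interest. The reasons listed beneath it include "Lack of efficacy" and "Protocol deviation (including noncompliance with study drug or study procedures)". Section 7.2 words the discretion differently: "subjects may be withdrawn at any time at the discretion of the Investigator or Enanta Pharmaceuticals, Inc. for safety, behavioral, or administrative reasons". It does not name efficacy, and it asks for consultation with the Medical Monitor where possible. Section 5.7.2 covers subjects whose dosing noncompliance continues despite education. It asks the Investigator to contact a Medical Monitor to "discuss possible discontinuation of the subject from the study".

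**What happens next.** Early stopping of treatment (Section 7.1.2) and early exit from the study (Section 7.1.3) lead to the same step, end-of-study procedures within 24 to 48 hours. Sections 7.2 and 7.2.2 and Appendix 1 note b repeat this. Appendix 1 note o has the diary device returned at the end-of-study visit. Withdrawn subjects are not replaced (Section 7.2).

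**What the analysis needs and does.** The primary endpoint is the TSS AUC from Day 1 through Day 14, while dosing ends on Day 5. SAP 3.14.1 requires only two scores for an AUC and uses the available ones. For subjects whose scores stop early: "The AUC is also standardized for 14 days by multiplying" it by 14/t_last. SAP 3.3 does not impute missing data in general.

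**The concern.** Leaving the study and stopping study drug are different events. The protocol (Section 11.4) and SAP 3.7 count them separately, so the phrase about discontinuation from the study cannot be read as loose wording for stopping tablets. After Day 5 there is no study treatment left to stop. A discontinuation for lack of efficacy from Day 6 onward can therefore only end measurement, and its trigger is the quantity that the primary endpoint measures. Noncompliance is not the outcome, but it is a post-randomisation event that may be related to symptoms.

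At stake is how informative the missing scores are. If exits follow symptoms, the truncated diaries are not a random sample, and the 14/t_last rule carries the average score before exit forward to Day 14. If the drug works and symptoms fall after exit, lack-of-efficacy exits would tend to occur more often on placebo and raise that arm's mean AUC.

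**Working it through.** **The plan's own figure.** Protocol Section 11.2 assumes means (SD) of 500 (450) and 225 (200), and a t-test with unequal variance. With two-sided alpha 0.05 (Section 11.1), 27 per arm gives 80.6% power (Satterthwaite df 35.9), so the stated 80% reproduces. Allowing for 20% dropout, 27/0.8 = 33.75, against the stated 35 or so per arm. The point does not turn on this calculation; it supplies the arm size and planned dropout used for scale below.

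**What the scaling does.** Let t be the elapsed day of the last score, m_b the average score before it and m_a the average that would have followed.

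- Scaled AUC = 14 × m_b
- Full AUC = t × m_b + (14 − t) × m_a
- The scaled value is too high if m_a < m_b, correct if they are equal, and too low if m_a > m_b.

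**Illustrations.** No symptom curve is given in the documents, so every curve here is an assumption. The ratio to the full-follow-up value is in brackets.

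| Assumed course of TSS | Full AUC | Exit day 5 | Exit day 9 |
|---|---|---|---|
| Linear, 15 to 0 by day 10 | 75 | 157.5 (2.10) | 115.5 (1.54) |
| Linear, 15 to 0 by day 14 | 105 | 172.5 (1.64) | 142.5 (1.36) |
| From 15, halving every 2 days | 44.6 | 100.0 (2.24) | 64.5 (1.45) |
| From 15, halving every 5 days | 95.0 | 151.5 (1.60) | 120.0 (1.26) |
| 12 rising to 20 at day 3, then linear to 2 at day 13.5 | 169.6 | 236.8 (1.40) | 213.3 (1.26) |
| Flat at 15 | 210 | 210 (1.00) | 210 (1.00) |
| Linear, 10 rising to 20 by day 14 | 210 | 165 (0.79) | 185 (0.88) |

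Worked lines:

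- First row: AUC(0 to t) = 15t − 0.75t². At t = 5 this is 56.25, and 56.25 × 14/5 = 157.5. At t = 9 it is 74.25, and 74.25 × 14/9 = 115.5.
- Second row: AUC(0 to t) = 15t − 15t²/28. At t = 5 this is 61.6, giving 172.5. At t = 9 it is 91.6, giving 142.5.
- Halving and rise-then-fall rows: trapezoid on half-day scores, with the full value taken to day 13.5 and scaled by 14/13.5.
- Flat row: 15 × 5 × 14/5 = 15 × 14 = 210.
- Last row: the average to day 5 is 10 + (10/14) × 2.5 = 11.79, and × 14 = 165. The average to day 9 is 10 + (10/14) × 4.5 = 13.21, and × 14 = 185.

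**Effect on an arm mean.** If a share f of one arm exits with ratio r, and those subjects' full AUC would have equalled the arm mean, the mean is multiplied by 1 + f(r − 1).

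- 1 of 35 with r = 1.5: 1 + (1/35) × 0.5 = 1.014, or +1.4%
- 10% with r = 1.5: +5%
- 20% with r = 2: +20%. This would need the whole planned dropout in that arm to be of this kind.

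The documents give no basis for choosing f.

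**The case against.** **The wording is permissive.** Discontinuation needs a judgement that continuing is not in the subject's best interest. The list also contains plain outcomes such as loss to follow-up and sponsor termination, so it reads partly as disposition codes. Lack of efficacy may be the subject's own reason for leaving. Section 7.2 does not name efficacy, and Section 5.7.2 goes no further than a discussion of possible discontinuation. All of this stands. A reader might infer that non-responders or subjects who miss doses must be removed; the documents do not say so.

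**The direction of bias is open.** A subject judged a non-responder may be the one whose symptoms persist, and for flat symptoms the scaled value equals the full one. Investigators are blinded, so under no treatment effect such exits should balance between arms. This also stands. A reader might infer that the rule must exaggerate the drug effect. That needs declining symptoms after exit and more exits on placebo, and the documents establish neither.

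**Noncompliant subjects are not dropped from the primary analysis.** The SAP 3.5 mITT definition has no compliance condition, and SAP 3.8 treats poor compliance as a ground for possible per-protocol exclusion. That is correct; what can be lost is their later diary data.

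**A missing-data analysis exists.** Protocol Section 11.6.2 plans multiple imputation as a sensitivity analysis. SAP 3.14.1.1 does not carry it over, which is a separate matter. Imputation would not replace scores that could have been collected.

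**No sentence says that the diary stops.** True. It is inferred from the end-of-study visit, the device return and the absence of any provision to continue.

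**Conclusion.** The concern holds as a gap in the withdrawal provisions. The protocol permits exit from the study with lack of efficacy and noncompliance among the listed reasons, and neither document provides for diary collection to Day 14 afterwards. Primary-endpoint data can therefore end for reasons related to symptoms or to post-randomisation behaviour. The same end-of-study path applies to subjects who only stop study drug.

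For an affected subject, the scaled AUC is about 1.3 to 2.2 times the full value for exit at day 5 to 9 under the declining curves assumed here. It is unbiased for flat symptoms and too low for worsening ones. The net effect on the treatment comparison cannot be fixed in size or sign from the documents. The number of such exits is unknown and, in a 14-day study, may be small. This is an inexpensive improvement worth making, not evidence that the primary comparison is invalid.

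**What to change.** 1. In the Summary (Subject Withdrawal) and Sections 5.7.2, 7.2 and 7.2.1, separate discontinuation of study drug from discontinuation of the study.
2. State that non-response, missed doses or protocol deviations do not by themselves end diary and swab collection. Both continue on the existing schedule to Day 14 for subjects who consent.
3. Reconcile the reason list in the Summary and Section 7.2.1 with the differently worded discretion in Section 7.2. Bring the end-of-study and device-return path (Sections 7.1.2, 7.1.3, 7.2 and 7.2.2; Appendix 1 notes b and o) into line with item 2.
4. Keep lack of efficacy and noncompliance as recorded reasons, for stopping drug or for a subject's own withdrawal. Deleting them would hide informative dropout under other codes.

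Best-interest and safety exits, and all decisions about study drug, are unchanged. The cost is protocol and eCRF wording, and some continued follow-up contact with subjects who would otherwise have left. The Day 14 schedule already exists, so no new visit or assessment type is needed.

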1. INTRODUCTION

1.1 Overview

EDP-938 [REDACTED] is a novel orally administered non-fusion replication inhibitor of respiratory syncytial virus (RSV) that is being developed as a potential treatment for RSV infection. This Phase 2b study, EDP 938-102, is a randomized, double-blind, placebo-controlled, multicenter study designed to assess the efficacy and safety of EDP-938 compared to placebo in ambulatory adult subjects with RSV infection.

1.2 Background

Respiratory syncytial virus is the leading cause of lower respiratory tract infection and presents a significant health challenge in small children, elderly, and immunocompromised patients (*Falsey et al., 2005; Hall et al., 2009; Shook and Lin, 2017*). The incidence and mortality due to RSV-associated acute lower respiratory illness (ALRI) varies substantially from year to year in any given population. Recently, Shi et al reported that in 2015, globally, 33.1 million episodes of RSV-ALRI resulted in about 3.2 million hospital admissions, and 59,600 in-hospital deaths in children younger than 5 years (*Shi et al., 2017*). In children younger than 6 months, RSV-ALRI was also responsible for 1.4 million hospital admissions, and 27,300 in-hospital deaths. Overall RSV-ALRI mortality could be as high as 118,200 in young children (*Shi et al., 2017*). In the United States, RSV infection is the most common cause of hospitalization in infants (*Hall et al., 2009; Nair et al., 2010*).

[REDACTED]

To address the unmet medical need for more effective antiviral therapies for RSV and based on the promising early nonclinical safety and pharmacological profile, Enanta Pharmaceuticals, Inc. is investigating EDP-938 in humans as a potential treatment for RSV infection.

1.3 Nonclinical Studies

A summary of nonclinical studies is provided below. Additional information can be found in the Investigator's brochure.

1.3.1 Nonclinical Pharmacology

EDP-938 is a novel non-fusion replication inhibitor of RSV. [REDACTED]

[REDACTED]

1.3.2 Nonclinical Pharmacokinetics

[REDACTED]

[REDACTED]

[REDACTED]

[REDACTED]

1.3.3 Safety Pharmacology

No safety pharmacology concerns have been identified following EDP-938 administration. [REDACTED]

[REDACTED]

[REDACTED]

1.3.4 Nonclinical Toxicology

[REDACTED]

[REDACTED]

[REDACTED]

[REDACTED]

1.4 Clinical Studies

[figure not shown]
Four Phase 1 clinical studies, including a first-in-human (FIH) study in healthy subjects, two drug-drug interaction studies, and a bioavailability study, as well as one Phase 2a study are ongoing as shown in [Table 1](#).

Table 1: List of Clinical Studies With EDP-938

Study Number	Study Title	Study Phase	Status
EDP-938-001	A Randomized, Double-Blind, Placebo-Controlled, First-In-Human Study of Orally Administered EDP-938 to Evaluate the Safety, Tolerability, and Pharmacokinetics of Single Ascending Doses (SAD), Multiple Ascending Doses (MAD) and the Effect of Food on EDP-938 Pharmacokinetics in Healthy Subjects	1	[REDACTED]
EDP 938-002	A Non-Randomized, Open-Label, Two-Part, Drug-Drug Interaction Study to Evaluate the Effects of Cyclosporine and Prednisone on the Pharmacokinetics and Safety of EDP-938 in Healthy Adult Subjects	1	[REDACTED]
EDP 938-003	A Non-Randomized, Open-Label, Three-Part, Drug-Drug Interaction Study to Evaluate the Effects of Itraconazole, Rifampin, and Quinidine on the Pharmacokinetics and Safety of EDP-938 in Healthy Subjects	1	[REDACTED]
EDP 938-004	A Randomized, Single-Dose, Open-Label, 3-Way, 3-Period Crossover, 6-Sequence Bioavailability Study Comparing the Pharmacokinetics of EDP-938 Suspension (Reference) to Tablet (Test) in Healthy Human Subjects under Fed and Fasted Conditions	1	[REDACTED]
EDP 938-101	A Randomized, Phase 2a, Double-Blind, Placebo-Controlled study to Evaluate the Safety, Pharmacokinetics and Antiviral Activity of Multiple Doses of Orally Administered EDP-938 Against Respiratory Syncytial Virus Infection in the Virus Challenge Model	2a	[REDACTED]

1.5 Potential Risks and Benefits

Potential risks to subjects receiving EDP-938 have been estimated based on safety data from the ongoing Phase 1 studies (EDP-938-001, EDP 938-002, EDP 938-003, and EDP 938-004) conducted in healthy subjects and the ongoing Phase 2a study (EDP 938-101) in healthy adult subjects infected with RSV A Memphis 37b.

[REDACTED]

In the Phase 2a EDP 938-101 study, both EDP-938 regimens (600 mg once daily or a 500 mg loading dose [LD] followed by 300 mg twice daily for 5 days) were generally well tolerated with safety profiles that were comparable to placebo. Among EDP-938 recipients, all events were reported as mild except for an event of moderate dyspepsia that was considered unrelated and resolved. No SAEs or AEs that led to study drug discontinuation were reported. Although the events of dizziness, headache, and diarrhea were numerically more common in EDP-938 recipients, these were infrequent, mild, and resolved.

Across these studies, EDP-938 has been observed to be safe and generally well tolerated with AEs being infrequent, generally mild, and resolving in follow-up. No definitive pattern of AEs has been observed to date. There have been no SAEs or severe AEs, with a single subject discontinuing study drug as noted above.

2. OBJECTIVES AND ENDPOINTS

2.1 Objectives

2.1.1 Primary Objective

- To evaluate the effect of EDP-938 on the progression of RSV infection by assessment of clinical symptoms

2.1.2 Secondary Objectives

- To evaluate the antiviral efficacy of EDP-938
- To evaluate the PK of EDP-938
- To evaluate the safety of EDP-938

[REDACTED]

2.2 Endpoints

2.2.1 Primary Endpoint

- Effect of EDP-938 compared to placebo on RSV infection clinical symptoms measured as the total symptom score (TSS) AUC from Day 1 through Day 14

2.2.2 Secondary Endpoints

- The AUC for RSV RNA viral load measured in nasopharyngeal swab samples by quantitative reverse transcription polymerase chain reaction (RT-qPCR)
- Percentage of subjects with RSV RNA viral load below the lower limit of quantitation in subjects receiving EDP-938 compared to placebo

- Plasma PK concentrations of EDP-938 and its major metabolites (EP-024636, EP-024594, and EP-024595)
- Safety endpoints include, but are not limited to, AEs, vital sign measurements, pulse oximetry measurements, and clinical laboratory test results (including chemistry, hematology, and urinalysis)
- Time to RSV RNA viral load below the lower limit of quantitation in subjects receiving EDP-938 compared to placebo
- RSV RNA viral load change from baseline

[REDACTED]

[REDACTED]

[REDACTED]

[REDACTED]

[REDACTED]

[REDACTED]

